## Statistical Analysis Plan

PROTOCOL D1052024  
 Page 30 of 66

---

AUC 0-144	Area under the concentration-time curve in serum from time zero (predose) to 144 hours postdose (ng·h/mL), calculated by linear up log down trapezoidal summation (lurasidone only).  For the calculation of AUC 0-144 , the concentration collected for the 144-hour timepoint and the actual sampling time will be used for calculating the partial area.
CL/F	Apparent systemic clearance (L/h) calculated as Dose/AUC 0-inf (lurasidone only).
V z /F	Apparent volume of distribution (L) calculated as Dose/AUC 0-inf /λ z (lurasidone only).
MRC max	After oral dosing (Day -7 only), the ratio of metabolites (ID-14283, ID-14326, ID-11614, ID-20219, and ID-20220) C max (mC max ) to parent (lurasidone HCl) C max (pC max ) calculated as: mC max divided by pC max (each ratio will be multiplied by 529.14 (MW of lurasidone HCl)/ 508.68, 508.68, 219.31, 305.37, or 321.37 (MW of ID-14283, ID-14326, ID-11614, ID-20219, and ID-20220, respectively, to correct for the difference in molecular weight of the parent and the metabolites).  After injectable suspension dosing (Day 1), the ratio of metabolites (ID-14283, ID-14326, ID-11614, ID-20219, and ID-20220) C max (mC max ) to parent (lurasidone injectable suspension) C max (pC max ) calculated as: mC max divided by pC max (each ratio will be multiplied by 492.68 (MW of lurasidone)/ 508.68, 508.68, 219.31, 305.37, or 321.37 (MW of ID-14283, ID-14326, ID-11614, ID-20219, and ID-20220, respectively, to correct for the difference in molecular weight of the parent and the metabolites).  All metabolites will be expressed as free base after dosing.
MRAUC 0-inf	The ratio of metabolites (ID-14283, ID-14326, ID-11614, ID-20219, and ID-20220) AUC 0-inf (mAUC) to parent (lurasidone injectable suspension) AUC 0-inf (pAUC) calculated as: mAUC divided by pAUC (each ratio will be multiplied by 492.68 (MW of lurasidone)/ 508.68, 508.68, 219.31, 305.37, or 321.37 (MW of ID-14283, ID-14326, ID-11614, ID-20219, and ID-20220, respectively, to correct for the difference in molecular weight of the parent and the metabolites).

The following serum PK parameters will be calculated for diagnostic purposes and listed only:

t 1/2 , Interval	The time interval (h) of the log-linear regression to determine λ z .
t 1/2 , N	Number of data points included in the log-linear regression analysis to determine λ z . A minimum of 3 data points will be used for determination.
Rsq	Coefficient of determination (goodness-of-fit statistic for calculation of λ z ). If value is less than 0.800, then t 1/2 , λ z , AUC 0-inf , CL/F, and V z /F will be listed but not included in summary presentations or statistical analyses
%AUCex	Percentage of AUC 0-inf obtained by extrapolation, calculated as:

---

Document:

Author:

Version Number:  
 Version Date:

Final Draft  
 11APR2019

Template No: CS\_TP\_BS016 Revision 4  
 Effective Date: 01Apr2016

Reference: CS\_WI\_BS005

$[(C_{last}/\lambda_z)/ AUC_{0-inf} \times 100]$ . If the extrapolated area ( $C_{last}/\lambda_z$ ) is greater than 20% of  $AUC_{0-inf}$ , then  $AUC_{0-inf}$ ,  $CL/F$ , and  $V_z/F$  will be listed but not included in summary presentations or statistical analyses.

Scatter plots of individual and geometric mean values versus lurasidone dose will be presented for  $C_{max}$ ,  $AUC_{0-last}$ , and  $AUC_{0-inf}$  for lurasidone and metabolites (ID-14283, ID-14326, ID-11614, ID-20219, and ID-20220).

### 17.2.2. URINE PARAMETERS AND DERIVATION

$A_{et1-t2}$  Amount of lurasidone and metabolites (ID-14283, ID-14326, and ID-11614) (ng) excreted in urine from  $t_1$  to  $t_2$  where  $t_1$  to  $t_2$  = 0-24, 24-48, 48-72, 72-96, 96-120, and 120-144 hours, calculated as the product of urine volume and urine concentration determined for each interval. If the concentration is BLQ, the concentration will be set to 0.

Cum  $A_{et1-t2}$  Cumulative amount of lurasidone and metabolites (ID-14283, ID-14326, and ID-11614) excreted in urine (ng) from  $t_1$  to  $t_2$  where  $t_1$  = 0 and  $t_2$  = 24, 48, 72, 96, 120, and 144 hours, calculated as the summation of  $A_e$  for each collection interval. This will include the overall cumulative  $A_e$  (ie,  $A_{e,0-144}$ ).

$CLR$  Renal clearance for lurasidone during the time interval 0 (predose) to 144 hours is calculated as:

$$CLR = A_{e,0-144}/AUC_{0-144}$$

$f_e$  Percent of administered lurasidone excreted unchanged in urine during the time interval  $t_1$  to  $t_2$  where  $t_1$  to  $t_2$  = 0-24, 24-48, 48-72, 72-96, 96-120, and 120-144 hours, calculated as:

$$f_e = (A_{et1-t2}/Dose) * 100$$

Cum  $f_{et1-t2}$  Cumulative percent of lurasidone excreted unchanged in urine during the time interval  $t_1$  to  $t_2$  where  $t_1$  = 0 and  $t_2$  = 24, 48, 72, 96, 120, and 144 hours calculated as the summation of  $f_e$  for each collection interval. This will include the overall cumulative  $f_e$  (i.e.,  $f_{e,0-144}$ ).

Graphical display of mean Cum  $A_e$  versus time, using the endpoint of the time interval, for lurasidone and metabolites (ID-14283, ID-14326, and ID-11614) will be presented by dose group and analyte.

All serum and urine PK parameter summaries will be presented by analyte, dose level, and subdivided by gender, as appropriate.

---

Document:

Author:

Version Number:  
 Version Date:

Final Draft  
 11APR2019

Template No: CS\_TP\_BS016 Revision 4  
 Effective Date: 01Apr2016

Reference: CS\_WI\_BS005

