6. INVESTIGATIONAL PLAN

6.1. Overall Study Design

This is a single-center, randomized, double-blind, placebo-controlled, inpatient, single ascending dose (SAD) study designed to evaluate the safety, tolerability, and PK of lurasidone injectable suspension in subjects with schizophrenia. This study will determine the minimum intolerable dose (MID), the maximum tolerated dose (MTD) of lurasidone injectable suspension, and characterize the PK profiles of lurasidone metabolites in serum (ID-14283, ID-14326, ID-11614, ID-20219, and ID-20220) and urine (ID-14283, ID-14326, and ID-11614) in this subject population. The potential effects of gender on the PK of lurasidone injectable suspension and its metabolites will also be evaluated when applicable.

A study schematic is presented in Figure 1. Details of the study assessments and other procedures to be performed at each visit are presented in Table 2, Schedule of Assessments, and Section 10, Study Assessments. The maximum duration for study participation for each subject will be up to approximately 96 days. If necessary, subjects may return to the clinic at any time for an unscheduled visit.

Figure 1: Study Schematic

^a Eligible subjects must be washed out/tapered off of their current antipsychotic medications 5 to 6 half-lives prior to Day -8 (may begin as early as Day -19). Subjects are required to be inpatient from Day -12 to Day 15 (for treatment and observation) and Day 29 to Day 33 (for restabilization to previous medications). Subjects may remain inpatient up to Day 33 (at the Investigator's discretion).

Subjects with schizophrenia who provide informed consent to participate in the study will undergo screening procedures and assessments between Days -35 to -13 to determine study eligibility.

b Subjects will receive 2 oral lurasidone 80 mg doses (Days -7 and -6) and be assessed for safety and tolerability for 5 days (Days -5 to -1) and to allow appropriate time to washout of the oral lurasidone dose.

^c Randomization occurs on Day 1. Cohort 1 will receive a single lurasidone injectable suspension dose of 30 mg or a single placebo injection dose; thereafter, single lurasidone injectable suspension doses of 75, 150, 300, and 450 mg may be administered (cohorts 2-5).

^d Subjects will be monitored for safety after the single lurasidone injectable suspension or placebo injection dose until Day 29. Subjects may be discharged on Day 15 at the Investigator's discretion.

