## **4. STUDY DESIGN**

### **4.1. GENERAL DESCRIPTION**

This is a single-center, randomized, double-blind, placebo-controlled, inpatient, single ascending dose (SAD) study designed to evaluate the safety, tolerability, and PK of lurasidone injectable suspension in subjects with schizophrenia. This study will determine the minimum intolerable dose (MID), the maximum tolerated dose (MTD) of lurasidone injectable suspension and characterize the PK profiles of lurasidone metabolites in serum (ID-14283, ID-14326, ID-11614, ID-20219, and ID-20220) and urine (ID-14283, ID-14326, and ID-11614) in this subject population. The potential effects of gender on the PK of lurasidone injectable suspension and its metabolites will also be evaluated when applicable.

Subjects will receive oral lurasidone 80 mg tablets on Day -7 and Day -6 (one dose per day), and be monitored for 5 days to ensure the subject is able to tolerate lurasidone (ie, absence of moderate adverse events). Subjects who tolerate dosing with oral lurasidone 80 mg will be eligible for randomization to receive a single lurasidone injectable suspension or placebo injection on Day 1.

The study is planned to include up to 5 cohorts. A total of 8 subjects (6 active and 2 placebo) will be dosed in each cohort. Lurasidone injectable suspension dosing will be initiated at 30 mg given as an intramuscular (IM) injection. Subsequent cohorts are planned to be dosed at 75, 150, 300, and 450 mg IM. Dose strengths after the first dose level may be modified based on safety assessments and exposure to lurasidone injectable suspension.

All 5 planned dose cohorts may not be used, depending on the dose escalation strategy employed. Additional cohorts may be included in this study, as necessary, and determined following a review of safety and exposure of lurasidone injectable suspension. Planned dose levels may be modified or repeated based on the overall safety profile of the current and/or previous cohorts.

---

Document:

Author:

[figure not shown]
Version Number:  
Version Date:

Final Draft  
11APR2019

Template No: CS\_TP\_BS016 Revision 4  
Effective Date: 01Apr2016

Reference: CS\_WI\_BS005

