## 7.9. EXAMINATION OF SUBGROUPS

Hemoglobin, hematocrit, uric acid, serum prolactin and QTcF will be presented by gender.

---

Document:

Author:

Version Number:  
 Version Date:

Final Draft  
 11APR2019

Template No: CS\_TP\_BS016 Revision 4  
 Effective Date: 01Apr2016

Reference: CS\_WI\_BS005

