## 17.3. DOSE PROPORTIONALITY

Dose proportionality assessment for lurasidone and metabolites (ID-14283, ID-14326, ID-11614, ID-20219, and ID-20220) for the administered dose range will be conducted using a power model for  $C_{max}$ ,  $AUC_{0\text{-last}}$ , and  $AUC_{0\text{-inf}}$ . The data will be fitted to a linear regression model:

$$\log(Y) = \alpha + \beta \log(X) + \varepsilon$$

where Y is the PK parameter, X is the dose,  $\varepsilon$  is the error term, and 'Log' represents the natural log. The estimate of the intercept and slope ( $\beta$ ), together with its 90% CI, will be presented. Scatter plots of the natural log of  $C_{max}$ ,  $AUC_{0\text{-last}}$ , and  $AUC_{0\text{-inf}}$  versus log dose, along with the fitted regression line, will be presented. Dose proportionality will be assessed based on the inclusion of 1.0 in the CI for slope.

The adequacy of the model will be examined graphically. If the fit of the linear regression model does not seem adequate, then pairwise comparisons between dose groups for lurasidone will be made for  $C_{max}$ ,  $AUC_{0\text{-last}}$ , and  $AUC_{0\text{-inf}}$  using the following one way ANOVA model on dose normalized log-transformed PK parameters with fixed effect for dose group and employing CIs for the difference in mean between dose groups:

$$\log \frac{Y_{ij}}{Dose_i} = \mu + Dose_i + \varepsilon_{ij}$$

where  $Y_{ij}$  is the PK parameter [either  $C_{max}$ ,  $AUC_{0\text{-last}}$ , or  $AUC_{0\text{-inf}}$ ] value for the  $i_{th}$  dose and  $j_{th}$  subject in that dose group,  $Dose_i$  is the  $i_{th}$  dose group, and  $\varepsilon_{ij}$  is the error term. No statistically significant difference between dose group means provides evidence of dose proportionality. From these analyses, for each PK analyte, least-squares (LS) mean for each dose group along with the corresponding 90% CI and LS mean for each pairwise dose group difference along the corresponding 90% CI in log-scale will be obtained. The results will be transformed back to the original scale by exponentiation to provide geometric LS mean for each dose group along with the associated 90% CI and geometric LS mean ratio along with the associated 90% CI for each pairwise ratio of dose groups.

Two additional models to assess dose proportionality will be completed in the same manner as stated above for the following dose ranges, 75 to 450 mg and 150 to 450 mg.

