## APPENDIX 4. LIST OF TABLES, FIGURES, AND LISTINGS

Number	Title
Table 14.1.1	Subject Disposition by Treatment - All Subjects
Table 14.1.2	Important Protocol Deviation (IPD) by Treatment - Injectable Safety Population
Table 14.1.3	Demographics and Baseline Characteristics by Treatment - Injectable Safety Population
Table 14.1.4.1	Medical History by Treatment - Injectable Safety Population
Table 14.1.4.2	Psychiatric History by Treatment - Injectable Safety Population
Table 14.1.5.1	Prior Medications by Treatment - Safety Population
Table 14.1.5.2	Concomitant Medications by Treatment - Safety Population
Table 14.2.1.1	Lurasidone Serum Concentrations (ng/mL) by Scheduled Timepoint and Dose Pharmacokinetic Population
Table 14.2.1.2	Metabolite Serum Concentrations (ng/mL) by Scheduled Time and Dose - Pharmacokinetic Population
Table 14.2.2.1	Lurasidone Serum Pharmacokinetic Parameters by Dose and Gender Following Lurasidone Injection - Pharmacokinetic Population
Table 14.2.2.2	Metabolite Serum Pharmacokinetic Parameters by Dose and Gender Following Lurasidone Injection - Pharmacokinetic Population
Table 14.2.3.1	Dose Proportionality Assessment - Lurasidone - Pharmacokinetic Population
Table 14.2.3.2	Dose Proportionality Assessment - Lurasidone Metabolites - Pharmacokinetic Population
Table 14.2.4.1	Lurasidone Urine Pharmacokinetic Parameters by Dose and Gender Following Lurasidone Injection - Pharmacokinetic Population
Table 14.2.4.2	Metabolite Urine Pharmacokinetic Parameters by Dose and Gender - Pharmacokinetic Population
Table 14.2.5	Positive and Negative Syndrome Scale (PANSS) Total Score: Actual and Change from Baseline by Scheduled Timepoint and Treatment - Pharmacodynamic Population
Table 14.3.1.1	Overall Summary of Adverse Events - Injectable Safety Population
Table 14.3.1.2	All Adverse Events by Treatment - Safety Population

---

Document:

Author:

Version Number:  
 Version Date:

Final Draft  
 11APR2019

Template No: CS\_TP\_BS016 Revision 4  
 Effective Date: 01Apr2016

Reference: CS\_WI\_BS005

Statistical Analysis Plan

PROTOCOL D1052024  
 Page 62 of 66

Number	Title
Table 14.3.1.3	All Adverse Events by Severity and Treatment - Safety Population
Table 14.3.1.4	All Adverse Events by Relationship to Treatment - Safety Population
Table 14.3.1.5	Duration of All Injection Site Reaction Related AEs in Days by Treatment - Injectable Safety Population
Table 14.3.2.1	All Serious Adverse Events by Treatment - Safety Population

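### The announced look at sex differences in PK rests on descriptive splits of about 6 active subjects per dose; an exploratory fit with a sex term would pool the comparison at little cost

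*SAP*

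**What the plan says.** Protocol 6.1 states: "The potential effects of gender on the PK of lurasidone injectable suspension and its metabolites will also be evaluated when applicable". The Protocol synopsis and SAP 4.1 say the same. Sex does not appear among the objectives (Protocol 4.1 and 4.2, SAP 3.1 and 3.2) or the PK endpoints (Protocol 5.2, SAP 3.3.2).

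The method is descriptive. Protocol 14.3.6 and SAP 17 call for PK summaries by dose level, split by sex. SAP 17.2.2 repeats this for all serum and urine parameters ("subdivided by gender, as appropriate"). SAP Appendix 4 lists matching tables, such as "Lurasidone Serum Pharmacokinetic Parameters by Dose and Gender Following Lurasidone Injection".

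SAP 17.3 does contain a model that uses all doses together: "The data will be fitted to a linear regression model", with log dose as the only predictor of the log parameter. The fallback ANOVA has dose group only. The subgroup section, SAP 7.9, names safety variables and no PK parameter: "Hemoglobin, hematocrit, uric acid, serum prolactin and QTcF will be presented by gender".

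On numbers, SAP 4.1 says "The study is planned to include up to 5 cohorts" and "A total of 8 subjects (6 active and 2 placebo) will be dosed in each cohort", but also "All 5 planned dose cohorts may not be used, depending on the dose escalation strategy employed".

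**The concern.** A sex comparison made separately in each dose divides six people in two. If few women enrol, many cells will be empty or hold one subject, for whom no SD exists. The reader of the report would then have to judge by eye whether five sparse tables point the same way.

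The information needed for a better answer is already collected. Sex is recorded at screening, and a regression across all doses is already planned. If the sex ratio is roughly constant over doses, one coefficient in that regression uses every active subject and yields a ratio with an interval. At stake is whether the announced evaluation produces an estimate that later studies can use. There is a secondary gain. Randomization numbers follow order of eligibility with no sex stratification described, so the sex mix can differ between cohorts, and a sex-adjusted slope shows whether that matters for dose proportionality.

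**Working it through.** **Inputs from the documents.** 5 cohorts × (6 + 2) = 40 dosed, which reproduces the planned maximum of 40 in the Protocol; active 5 × 6 = 30. Doses are 30, 75, 150, 300 and 450 mg. PK intervals are 90% (SAP 7.5). No precision target for a sex comparison is given, so there is no planned figure to reproduce for it.

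**Assumptions.** Neither document gives between-subject variability or a sex mix. I use a geometric CV of 30, 50 and 70%, with log SD σ = sqrt(ln(1 + CV²)) = 0.29, 0.47, 0.63, and a range of splits.

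**Formulas.** Within one dose: SE = σ·sqrt(1/nF + 1/nM), 4 df. Pooled: least squares for log(Y) = α + β·log(dose) + γ·sex, 27 df with 30 subjects. When sex is spread evenly over doses, this SE reduces to the same expression with the total counts. The 90% CI is the ratio times or divided by exp(t × SE).

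**Example at CV 50% (σ = 0.472).**
- 3 against 3 in one dose: SE = 0.816 × 0.472 = 0.386; t = 2.132; factor exp(0.822) = 2.28.
- 15 against 15 pooled: SE = 0.365 × 0.472 = 0.172; t = 1.703; factor exp(0.294) = 1.34.

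| Contrast | Women v men | CV 30% | CV 50% | CV 70% |
|---|---|---|---|---|
| One dose, hypothetical | 3 v 3 | 1.67 | 2.28 | 3.00 |
| One dose, hypothetical | 1 v 5 | 1.98 | 3.01 | 4.37 |
| Pooled, 30 active | 15 v 15 | 1.20 | 1.34 | 1.48 |
| Pooled, 30 active | 10 v 20 | 1.21 | 1.37 | 1.52 |
| Pooled, 30 active | 5 v 25 | 1.28 | 1.48 | 1.69 |
| Pooled, 30 active | 3 v 27 (one in each middle dose) | 1.36 | 1.63 | 1.93 |
| Pooled, first 3 cohorts, 18 active | 9 v 9 | 1.27 | 1.48 | 1.69 |
| Pooled, first 3 cohorts, 18 active | 3 v 15 | 1.38 | 1.69 | 2.01 |

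With dose as a factor plus sex (24 df), the CV 50% factors are 1.34, 1.37 and 1.49 for 15, 10 and 5 women. The gain therefore does not depend on the log-linear dose relation.

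**How sparse the cells would be.** By binomial probability, a dose of 6 has at least two of each sex with probability 0.11, 0.34, 0.57 and 0.78 when 10, 20, 30 and 50% of subjects are women. At 10%, the whole set of 30 has three or fewer women with probability 0.65 and none with probability 0.04, so even pooling may fail.

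**Cost to the slope.** At CV 50% the 90% CI half-width for β is 0.151 with or without sex when sex is balanced over doses. With women per dose of 0, 0, 2, 4, 4 the adjusted half-width is 0.189 (variance ratio 1.55). With 0, 1, 3, 5, 6 it is 0.228 (variance ratio 2.28).

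**The case against.** The strongest reply is that the plan does what the protocol prescribes. Protocol 14.3.6 asks for descriptive PK summaries split by sex, and the SAP supplies them. A reader might infer that the trial fails one of its own objectives, or that the SAP departs from the protocol. The documents support neither: sex is absent from the objectives and endpoints, and the design sentence speaks only of potential effects, evaluated where applicable. That part of the reply stands.

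Second, the SAP plans no interval for a sex ratio within a dose. The factors 2.28 and 3.01 describe a contrast constructed here to show how little one dose can say; they are not a loss in a planned result. That also stands.

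Third, the pooled figure depends on who enrols. The 1.34 is the best split at one assumed CV. Fewer cohorts, exclusions from the PK population, or AUC_0-inf values dropped under the R-squared and extrapolation rules of SAP 17.2.1 would widen it. With three women, approximate power for a 1.5-fold ratio at CV 50% is only 0.41. Hence the need for a minimum per sex.

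Fourth, a reader might take the extra term to be free. It costs one residual degree of freedom under balance, but more when sex clusters by dose, which nothing in the design prevents. Fifth, six analytes by three parameters give 18 ratios. With no true effect, 18 × 0.10 = 1.8 intervals would be expected to exclude 1.

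These points limit the claim and shape the fix. They do not supply a pooled sex comparison, which remains absent.

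**Conclusion.** The point holds as a low-cost improvement. Both documents announce an evaluation of sex effects on PK, and every planned output for it is a descriptive split within a dose of about six active subjects. A pooled sex term on the same data would give a 90% CI factor of 1.20 to 1.48 with 15 women among 30 active subjects, and 1.28 to 1.69 with 5, over CVs of 30 to 70%. With 3 women it is weak (1.36 to 1.93). All of this rests on assumed CVs and sex mixes and on one sex ratio common to all doses.

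It would go too far to conclude that the planned dose-proportionality analysis is wrong or should be replaced by the adjusted one. Under clustering the adjusted slope is less precise, so the dose-only model should stay as the stated analysis.

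**What to change.** In SAP 17.3, leave the dose-only power model unchanged as the dose-proportionality analysis and add a paragraph that specifies:

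- An exploratory fit log(Y) = α + β·log(dose) + γ·sex for C_max, AUC_0-last and AUC_0-inf.
- For lurasidone, the female/male geometric mean ratio exp(γ) with its 90% CI. Any metabolite ratios are labelled exploratory and unadjusted for multiplicity.
- The sex-adjusted slope, shown as supportive only.
- If the power model is judged inadequate, a model with dose as a factor plus sex.
- A minimum number per sex, for example about 5 of the minority sex in the PK population and not all in one cohort. Below it, only the descriptive tables and listings are given. This would give the qualifier in the design text a concrete meaning.

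Keep the descriptive tables by dose and sex; they remain the only sex display for half-life, CL/F, V_z/F and the urine parameters.

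The cost is one extra fit per parameter and a short table, with no new data. Statistically it is one residual degree of freedom when sex is balanced over doses. When sex clusters strongly, the adjusted slope has a wider interval (half-width 0.151 rising to about 0.19 to 0.23 at CV 50%), which leaves the planned dose-only result untouched.

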## 17.3. DOSE PROPORTIONALITY

Dose proportionality assessment for lurasidone and metabolites (ID-14283, ID-14326, ID-11614, ID-20219, and ID-20220) for the administered dose range will be conducted using a power model for  $C_{max}$ ,  $AUC_{0\text{-last}}$ , and  $AUC_{0\text{-inf}}$ . The data will be fitted to a linear regression model:

$$\log(Y) = \alpha + \beta \log(X) + \varepsilon$$

where Y is the PK parameter, X is the dose,  $\varepsilon$  is the error term, and 'Log' represents the natural log. The estimate of the intercept and slope ( $\beta$ ), together with its 90% CI, will be presented. Scatter plots of the natural log of  $C_{max}$ ,  $AUC_{0\text{-last}}$ , and  $AUC_{0\text{-inf}}$  versus log dose, along with the fitted regression line, will be presented. Dose proportionality will be assessed based on the inclusion of 1.0 in the CI for slope.

The adequacy of the model will be examined graphically. If the fit of the linear regression model does not seem adequate, then pairwise comparisons between dose groups for lurasidone will be made for  $C_{max}$ ,  $AUC_{0\text{-last}}$ , and  $AUC_{0\text{-inf}}$  using the following one way ANOVA model on dose normalized log-transformed PK parameters with fixed effect for dose group and employing CIs for the difference in mean between dose groups:

$$\log \frac{Y_{ij}}{Dose_i} = \mu + Dose_i + \varepsilon_{ij}$$

where  $Y_{ij}$  is the PK parameter [either  $C_{max}$ ,  $AUC_{0\text{-last}}$ , or  $AUC_{0\text{-inf}}$ ] value for the  $i_{th}$  dose and  $j_{th}$  subject in that dose group,  $Dose_i$  is the  $i_{th}$  dose group, and  $\varepsilon_{ij}$  is the error term. No statistically significant difference between dose group means provides evidence of dose proportionality. From these analyses, for each PK analyte, least-squares (LS) mean for each dose group along with the corresponding 90% CI and LS mean for each pairwise dose group difference along the corresponding 90% CI in log-scale will be obtained. The results will be transformed back to the original scale by exponentiation to provide geometric LS mean for each dose group along with the associated 90% CI and geometric LS mean ratio along with the associated 90% CI for each pairwise ratio of dose groups.

Two additional models to assess dose proportionality will be completed in the same manner as stated above for the following dose ranges, 75 to 450 mg and 150 to 450 mg.

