## 7.5. STATISTICAL TESTS

90% CIs will be used for the PK analysis.

---

Document:

Author:

Version Number:  
Version Date:

Final Draft  
11APR2019

Template No: CS\_TP\_BS016 Revision 4  
Effective Date: 01Apr2016

Reference: CS\_WI\_BS005

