### 17.2.1. SERUM PARAMETERS AND DERIVATION

The following serum PK parameters will be estimated by noncompartmental methods for lurasidone and metabolites (ID-14283, ID-14326, ID-11614, ID-20219, and ID-20220) using actual elapsed time from dosing on Day 1 following injectable suspension administration unless noted otherwise:

$C_{max}$	Maximum concentration in serum (ng/mL), obtained directly from the observed concentration versus time data (Day -7 and Day 1).
$t_{max}$	Time of maximum concentration (h), obtained directly from the observed concentration versus time data (Day -7 and Day 1).
$C_{last}$	The last postdose quantifiable serum concentration (ng/mL).
$t_{last}$	Time of the last postdose quantifiable serum concentration (h).
$\lambda_z$	Terminal rate constant (1/h), determined by linear regression of the terminal points of the log-linear concentration-time curve. Visual assessment will be used to identify the terminal linear phase of the concentration-time profile.
$t_{1/2}$	Terminal half-life, calculated as $\ln(2)/\lambda_z$ .
$AUC_{0-last}$	Area under the concentration-time curve in serum from time zero (predose) to time of last quantifiable concentration (ng·h/mL), calculated by linear up log down trapezoidal summation.
$AUC_{0-inf}$	Area under the concentration-time curve in serum from time zero (predose) extrapolated to infinite time (ng·h/mL), calculated by linear up log down trapezoidal summation and extrapolated to infinity by addition of the last quantifiable concentration divided by the terminal rate constant: $AUC_{0-last} + C_{last}/\lambda_z$ .

---

Document:

Author:

Version Number:  
Version Date:

Final Draft  
11APR2019

Template No: CS\_TP\_BS016 Revision 4  
Effective Date: 01Apr2016

Reference: CS\_WI\_BS005

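### If low-dose profiles fall below the assay limit during sampling, the AUC0-last and AUC0-inf slopes can depart from 1 for a dose-proportional drug, and SAP 17.3 has no common-window AUC to show it

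*SAP*

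**What the plan says.** SAP 17.3 states that the assessment "for the administered dose range will be conducted using a power model for" Cmax, AUC0-last and AUC0-inf, fitting ln(parameter) on ln(dose). Its decision rule is "Dose proportionality will be assessed based on the inclusion of 1.0 in the CI for slope". SAP 7.5 sets the level: "90% CIs will be used for the PK analysis". Two further models are fitted "for the following dose ranges, 75 to 450 mg and 150 to 450 mg", and pairwise ANOVA comparisons follow if the fit looks inadequate. SAP 17.3 does not say which dose range governs the conclusion.

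SAP 17.2.1 defines AUC0-last as running "from time zero (predose) to time of last quantifiable concentration". AUC0-inf with more than 20% extrapolated area, or with Rsq below 0.800, "will be listed but not included in summary presentations or statistical analyses". The protocol's extrapolation limit (section 10.3) is 30%.

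SAP 17.2.1 also derives an AUC over a fixed window, "from time zero (predose) to 144 hours postdose", for lurasidone only; SAP 3.3.2 lists the same parameter for metabolites as well. SAP 17.2 gives rules for keeping AUC0-144 in, or excluding it from, inferential statistics. The opening text of SAP 17 identifies the inferential PK analysis as dose proportionality. Yet AUC0-144 does not appear in 17.3.

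**The concern.** The planned doses span 30 to 450 mg, a 15-fold range, for a slowly released depot. With the same profile shape at every dose, a lower dose reaches the assay limit (LLOQ) sooner. If that happens within the sampling period, AUC0-last covers less time at low doses, and its slope mixes dose with length of observation. The late samples are far apart (144, 336, 504, 672 and 1440 h), so losing one can remove a large area.

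AUC0-inf does not necessarily correct this. A profile cut short has more extrapolated area and fewer terminal points, so the exclusions can fall mainly on low doses. The low-dose subjects who remain tend to have the higher exposures, which pulls the slope down.

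At stake is the proportionality statement for two parameters the SAP calls primary. It could report more-than-proportional exposure on one and less-than-proportional on the other, with assay sensitivity as the only cause.

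**Working it through.** The plan states no slope, power or precision figure for this analysis, so there is nothing to reproduce. The check asks what the planned rules return when the true slope is exactly 1.

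**Inputs from the documents.** Doses 30, 75, 150, 300 and 450 mg; 6 active subjects per dose (SAP 4.1). Serum sampling to 1440 h (SAP 17.1.1). Linear-up log-down AUC, at least 3 terminal points, Rsq at least 0.800, extrapolation at most 20% (SAP 17.2.1). SAP 17.2 treats BLQ values after tlast as zero in one sentence and missing in another; AUC0-last ends at tlast either way.

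**Assumptions, because the documents give no figure.** Terminal half-life 100, 200, 350 or 600 h. R, the top-dose Cmax divided by LLOQ, 20, 50, 150, 500 or 2000. CV 40% for exposure and 30% for release rate; residual error 12%. Under proportionality the 30 mg ratio is R/15: about 1.3, 3.3, 10, 33 and 133.

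**Mechanism by hand.** A 15-fold dose adds log2(15) = 3.9 half-lives of quantifiable time, or 781 h at a half-life of 200 h. Take release half-life 200 h and elimination half-life 30 h (both assumed), with C(t) proportional to exp(-kr·t) - exp(-ke·t). The share of total AUC by time T is

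[(1 - exp(-kr·T))/kr - (1 - exp(-ke·T))/ke] / (1/kr - 1/ke).

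This gives 0.633 at 336 h and 0.885 at 672 h. Suppose tlast is 336 h at 30 mg and 672 h at the other four doses. Then ln(AUC0-last) at 30 mg is low by ln(0.885/0.633) = 0.336. On ln(dose), 30 mg lies 1.507 below the mean and the sum of squares is 4.706, so the slope shifts by 0.336 × 1.507 / 4.706 = 0.11. One late sample time lost between doses, from one cohort, gives a slope of 1.11.

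**Simulation.** A one-compartment depot with slow release was analysed by the SAP rules (best adjusted R² replacing visual choice of terminal points). The power model was fitted by least squares with a 90% t interval, using 600 trials per cell. Target: slope 1.00, with 90% of CIs containing 1.0. Full range, 30 to 450 mg:

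| R | AUC0-last slope (CI contains 1.0) | AUC0-inf slope (CI contains 1.0) |
|---|---|---|
| 20–50 | 1.11–1.30 (18–66%) | 0.80–0.94 (74–87%) |
| 150 | 1.01–1.06 (78–89%) | 0.95–0.99 (85–92%) |
| 500 or more | 0.99–1.04 (86–92%) | 0.99–1.01 (88–92%) |

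As an example, at half-life 200 h and R = 50, median tlast was 336 h at 30 mg and 672 h at every higher dose. AUC0-inf was kept in 15, 72, 84, 92 and 97% of subjects from the lowest dose to the highest. Slopes were 1.16 for AUC0-last (51% of CIs containing 1.0), 0.94 for AUC0-inf (84%) and 1.01 for AUC0-144 (91%).

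With the protocol's 30% limit, AUC0-inf slopes at R = 20–50 were 0.83–0.94. Cmax slopes there were 0.93–1.00.

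**Restricted ranges, AUC0-last.** At R = 50 the slope fell to 1.00–1.10 (75–450 mg) and 0.99–1.07 (150–450 mg). At R = 20 it stayed at 1.18–1.27 and 1.05–1.22.

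**Common window.** AUC0-144 gave 0.99–1.02 with 88–93% of CIs containing 1.0 in every cell with R of 50 or more. At R = 20 it gave 0.94–0.98 (85–90%), because 29–57% of 30 mg subjects were BLQ at 144 h and lost the parameter.

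**The case against.** The strongest reply is that nothing in the documents shows the condition is met. LLOQ and injection half-life are not stated, and R = 20 puts the 30 mg peak only about 1.3 times above the limit. With a sensitive assay, tlast is similar across doses and the problem nearly vanishes. This stands. A reader might infer that the plan will produce biased slopes; the documents support only that it can.

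AUC0-inf losses need not fall on low doses either. At a 600 h half-life with R of 150 or more, only 46–56% of values were kept, and that was so at every dose. This also stands.

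Safeguards exist. The 75–450 and 150–450 mg models drop the cohort most at risk, model adequacy is checked graphically, and Cmax is largely unaffected. Protocol 10.3 also lets later cohorts' sampling be revised using BLQ timing and half-life. These help, but at R = 20 the restricted models still did not always remove the bias, and the ANOVA fallback uses the same three parameters.

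AUC0-144 is a poor replacement. Under the hand model it holds 49% of total exposure at a release half-life of 100 h and 16% at 400 h. If release half-life lengthened from 200 h at 30 mg to 300 h at 450 mg (assumed) with total exposure exactly proportional, those shares would be 0.292 and 0.207. The two-dose slope would be 1 + ln(0.207/0.292)/ln(15) = 0.87. Protocol 3.1 says dissolution governs clearance from muscle, so dose-dependent release is plausible. This objection stands in full.

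Finally, tlast is already an endpoint, %AUCex and Rsq are listed, and excluded PK data have a listing. What is missing is their display by dose beside the slopes.

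**Conclusion.** The point holds as a conditional weakness. When low-dose profiles reach the LLOQ during sampling, AUC0-last can show a slope above 1 and AUC0-inf a slope below 1 for an exactly proportional drug. The size is about 1.11–1.30 and 0.80–0.94 at an assumed top-dose Cmax/LLOQ of 20–50, shrinking to little or nothing at 500 or more. These figures rest on the assumed half-lives, variability and dose-independent release.

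Two stronger readings fail. One is that metabolites must be worse affected: no document places them nearer the assay limit. The other is that AUC0-144 should become the basis of the conclusion: it reflects early release and can itself be lost at 30 mg.

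The consequence is limited. Dose proportionality is not a stated objective, and protocol 14.1 says the primary endpoints are safety. Even so, the plan as written cannot separate assay truncation from non-proportionality, and SAP 17.2 already anticipates an inferential use of AUC0-144 that 17.3 does not provide.

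**What to change.** In SAP 17.3, keep the prespecified parameters and make these changes:

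- Add, as a sensitivity analysis, the same power model on a common-window AUC: AUC0-144 for lurasidone, and AUC to the latest nominal time at which the lowest dose is still quantifiable. State how a BLQ value at the end of the window is handled.
- Beside each slope, show tlast and the number of AUC0-inf values excluded, by dose.
- State the reading in advance: if the AUC0-last or AUC0-inf slope disagrees with the common-window slope, and tlast or exclusions differ by dose, the departure from 1.0 is not attributed to non-proportionality.
- Reconcile SAP 3.3.2, which lists AUC0-144 for metabolites, with 17.2.1, which derives it for lurasidone only.

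The cost is a few lines of text and extra model runs on data already collected. The downside is that AUC0-144 covers only the early part of the depot profile, depends on release rate, and is lost at 30 mg if the 144 h sample is BLQ. It should therefore sit beside the prespecified parameters and not replace them.
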